6.6.3 Hospital Anxiety and Depression Scale (HADS)

The Hospital Anxiety and Depression Scale (HADS) is a fourteen-item scale that generates ordinal data. Seven of the items relate to anxiety and seven relate to depression. This outcome measure was specifically developed to avoid reliance on aspects of these conditions that are also common somatic symptoms of illness, for example fatigue and insomnia or hypersomnia. Calculations of scores: each of the 14 items is rated on a 4-point scale (‘Yes, definitely’, ‘Yes, sometimes’, ‘No, not much’ and ‘No, not at all’). All items except 7 and 10 are scored as ‘Yes, definitely’ = 3 to ‘No, not at all’ = 0. Items 7 and 10 are scored as ‘Yes, definitely’ = 0 to ‘No, not at all’ = 3. The HADS consists of two sub-scores: the HAD-A for anxiety and HAD-D for depression; each sub-score ranges from 0 to 21 points; scores ≥ 11 indicate the presence of anxious or depressive disorders; scores between 8-10 points are borderline abnormal, and scores of ≤ 7 indicate that the disorder is not present.

Patients will be asked to complete the questionnaire at visits 3, 10 and 12 of the core study and at visits 2 and 4 of the extension period.

Completed questionnaires will be reviewed and examined by the investigator before the clinical examination for responses that may indicate potential AEs or SAEs. The investigator should review not only the responses to the questions in the questionnaires but also any unsolicited comments written by the patient.

If the occurrence of AEs or SAEs is confirmed, the physician must record the events as per instructions given in [Section 7.2](#) of the protocol.

7 Safety monitoring

7.1 Adverse events

An adverse event (AE) is any untoward medical occurrence (i.e., any unfavorable and unintended sign [including abnormal laboratory findings], symptom or disease) in a subject or clinical investigation subject *after providing written informed consent* for participation in the study. Therefore, an AE may or may not be temporally or causally associated with the use of a medicinal (investigational) product.

The occurrence of adverse events should be sought by non-directive questioning of the patient at each visit during the study. Adverse events also may be detected when they are volunteered by the patient during or between visits, or through physical examination, laboratory tests, or other assessments.

Abnormal laboratory values or test results constitute adverse events only if they fulfill at least one of the following criteria:

- they induce clinical signs or symptoms,
- they are considered clinically significant,
- they require therapy.

Clinically significant abnormal laboratory values or test results should be identified through a review of values outside of normal ranges/clinically notable ranges, significant changes from baseline or the previous visit, or values that are considered non-typical in a patient with underlying disease. Investigators have the responsibility for managing the safety of individual patient and identifying adverse events. Alert ranges for labs and other test abnormalities are included in [Appendix 1](#).

Adverse events should be recorded in the Adverse Events CRF under the signs, symptoms or diagnosis associated with them accompanied by the following information.

- the severity grade
 - mild: usually transient in nature and generally not interfering with normal activities
 - moderate: sufficiently discomforting to interfere with normal activities
 - severe: prevents normal activities
- its relationship to the investigational treatment (no/yes)
- its duration (start and end dates) or if the event is ongoing an outcome of not recovered/not resolved should be reported.
- whether it constitutes a serious adverse event (SAE)
- action taken regarding the investigational treatment
- whether other medication or therapies have been taken (concomitant medication/non-drug therapy)
- its outcome (not recovered/not resolved; recovered/resolved; recovering/resolving, recovered/resolved with sequelae; fatal; or unknown)

A serious adverse event (SAE) is any adverse event (appearance of or worsening of any pre-existing) undesirable sign(s), symptom(s) or medical condition(s) which meets any one of the following criteria:

- is fatal or life-threatening
- results in persistent or significant disability/incapacity
- constitutes a congenital anomaly/birth defect
- requires inpatient hospitalization or prolongation of existing hospitalization, unless hospitalization is:
 - for a routine treatment or monitoring of the studied indication, not associated with any deterioration in condition
 - for an elective or pre-planned treatment for a pre-existing condition that is unrelated to the indication under study and has not worsened since signing the informed consent
 - for treatment on an emergency outpatient basis for an event not fulfilling any of the definitions of an SAE given above and not resulting in hospital admission
 - for social reasons and respite care in the absence of any deterioration in the patient's general condition
 - medically significant, i.e. defined as an event that jeopardizes the patient or may require medical or surgical intervention to prevent one of the outcomes listed above.

All malignant neoplasms will be assessed as serious under “medically significant” if other seriousness criteria are not met.

Unlike routine safety assessments, SAEs are monitored continuously and have special reporting requirements; see [Section 7.2](#).

All adverse events should be treated appropriately. Treatment may include one or more of the following: no action taken (i.e. further observation only); investigational treatment dosage adjusted/temporarily interrupted; investigational treatment permanently discontinued; concomitant medication given; and non-drug therapy given. The action taken to treat the adverse event should be recorded on the Adverse Event CRF.

Once an adverse event is detected, it should be followed until its resolution or until it is judged to be permanent. An assessment should be made at each visit (or more frequently, if necessary) of any changes in severity, the suspected relationship to the investigational treatment, the interventions required to treat it, and the outcome.

Information about common side effects already known about the investigational drug can be found in the Investigator Brochure (IB) or will be communicated between IB updates in the form of Investigator Notifications. This information will be included in the patient informed consent and should be discussed with the patient during the study as needed.

The investigator should also instruct each patient to report any new adverse event (beyond the protocol observation period) that the patient, or the patient's personal physician, believes might reasonably be related to study treatment. This information should be recorded in the investigator's source documents. However, if the AE meets the criteria of an SAE, it must be reported to Novartis.

7.2 Serious adverse event reporting

To ensure patient safety, every SAE, regardless of causality, occurring after the patient has provided informed consent and until 30 days after the last study visit must be reported to

Novartis within 24 hours of learning of its occurrence. Any SAEs experienced after the 30-day period should only be reported to Novartis if the investigator suspects a causal relationship to study treatment.

Recurrent episodes, complications, or progression of the initial SAE must be reported as follow-up to the original episode, regardless of when the event occurs. This report must be submitted within 24 hours of the investigator receiving the follow-up information. An SAE that is considered completely unrelated to a previously reported one should be reported separately as a new event.

The investigator will complete the SAE Report Form in English, assess the relationship to the study treatment and send the completed and signed form by fax within 24 hours to the local Novartis Drug Safety and Epidemiology Department Novartis (DS&E). The original and the duplicate copies of the SAE Form, and the fax confirmation sheet will be kept with the case report forms at the study site.

Follow-up information will be sent to the same person to whom the original SAE Form was sent, re-stating the date of the original report. A new SAE Form will be used (stating that this is a “follow-up”). The follow-up report should describe whether the event is resolved or continues, if and how it was treated, and whether the patient continued or discontinued study participation. The form and fax confirmation sheet will be retained at the study site.

If the SAE is not previously documented in the Investigator’s Brochure or Package Insert (new occurrence) and is thought to be related to the investigational treatment, a Drug Safety and Epidemiology Department associate may urgently require further information from the investigator for Health Authority reporting. Novartis may need to issue an Investigator Notification to inform all investigators involved in any study with the same investigational treatment that this SAE has been reported. Suspected Unexpected Serious Adverse Reactions (SUSARs) will be collected and reported to the competent authorities and relevant ethics committees in accordance with Directive 2001/20/EC or as per national regulatory requirements in participating countries.

7.3 Liver safety monitoring

To ensure patient safety and enhance reliability in determining the hepatotoxic potential of an investigational drug, a standardized process for identification, monitoring and evaluation of liver events has to be followed.

Liver events are divided into two categories:

- Liver events of special interest, which consist of liver function test (LFT) elevations.
- Medically significant liver events that are considered as serious adverse events and consist of marked elevations of LFTs and / or pre-specified adverse events.

Please refer to [Table 14-1](#) in [Appendix 2](#) for complete definitions of liver events.

Any liver event that meets the criteria for “**medically significant**” event, as outlined in [Table 14-1](#) of [Appendix 2](#), should follow the **standard procedures for SAE reporting** as described in [Section 7.2](#).

Every liver event as defined in [Table 14-1](#) of [Appendix 2](#) should be followed up by the investigator or designated personal at the trial site as summarized below.

- Repeat the LFT to confirm elevation as appropriate.
- Discontinue the investigational drug if appropriate.
- Hospitalize the patient if appropriate.
- Assess the causality of the liver event via exclusion of alternative causes (e.g., disease, co-mediations).
- An investigation of the liver event needs to be followed until resolution.

These investigations can include serology tests, imaging and pathology assessments, hepatology consultancy, based on the investigator's discretion. All follow-up information and the procedures performed should be recorded on appropriate CRF pages, including the liver event overview CRF pages.

7.4 Pregnancy reporting

To ensure patient safety, each pregnancy occurring while the patient is on study treatment must be reported to Novartis within 24 hours of learning of its occurrence. The pregnancy should be followed up to determine outcome, including spontaneous or voluntary termination, details of the birth, and the presence or absence of any birth defects, congenital abnormalities, or maternal and/or newborn complications.

Pregnancy should be recorded on a Clinical Trial Pregnancy Form and reported by the investigator to the local Novartis Drug Safety and Epidemiology Department. Pregnancy follow-up should be recorded on the same form and should include an assessment of the possible relationship to the investigational treatment.

Any SAE experienced during pregnancy must be reported on the SAE Report Form.

8 Data review and database management

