16. Abnormal laboratory results at screening: Liver tests: either aspartate aminotransferase (AST), alanine aminotransferase (ALT), or alkaline phosphatase (ALP) > 2.0 × upper limit of normal (ULN) or total bilirubin > 1.5 × ULN (except for subjects with Gilbert Syndrome).
17. White blood cell count < 3,000 cells/mm³ (< 3 × 10⁹/L in SI [international system] units).
18. Hemoglobin < 10 g/dL.
19. Subject is currently enrolled in another investigational study unless a washout period, as described in table 5-1, will be performed.
20. Donation or transfusion of blood, plasma, or platelets within 90 days prior to inclusion.
21. Pregnant or nursing (lactating) women, where pregnancy is defined as the state of female after conception until the termination of gestation, confirmed by a positive HCG laboratory test (> 10 mIU/mL).

22. Women of childbearing potential, defined as all women physiologically capable of becoming pregnant, must use effective contraception during the study and for 16 weeks after stopping treatment. Highly effective contraception methods include:

- Total abstinence (when this is in line with the preferred and usual lifestyle of the subject. Periodic abstinence (e.g., calendar, ovulation, symptothermal, post-ovulation methods) and withdrawal are not acceptable methods of contraception.
- Female sterilization (have had surgical bilateral oophorectomy with or without hysterectomy) or tubal ligation at least six weeks before taking study treatment. In case of oophorectomy alone, only when the reproductive status of the woman has been confirmed by follow up hormone level assessment.
- Male sterilization (at least 6 months prior to screening). For female subjects on the study, the vasectomized male partner should be the sole partner for that subject.
- Combination of any two of the following (a+b or a+c, or b+c):
 - a. Use of oral, injected or implanted hormonal methods of contraception or other forms of hormonal contraception that have comparable efficacy (failure rate <1%), for example hormone vaginal ring or transdermal hormone contraception.
 - b. Placement of an intrauterine device (IUD) or intrauterine system (IUS).
 - c. Barrier methods of contraception: condom or occlusive cap (diaphragm or cervical/vault caps) with spermicidal foam/gel/film/cream/vaginal suppository.

In case of oral contraception, women should have been stable on the same pill for a minimum of 3 months before taking study treatment.

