5.5.8 Prohibited Treatment

Use of the treatments displayed in [Table 5-1](#) is NOT allowed after screening.

If a prohibited treatment listed in [Table 5-1](#) is used during the study, the patient must discontinue use of the prohibited treatment if he/she wishes to continue in the study. At the discretion of the investigator, if the patient's use of a prohibited treatment presents undue safety risk for the patient, he/she should be discontinued from study treatment as per [Section 5.5.9](#). If the patient receives a live virus vaccination during the study, he/she must discontinue study treatment and enter the post-treatment follow up period.

Table 5-1: Prohibited treatment

Prohibited treatments	Washout period (before day 1)
Secukinumab or any other biologic drug directly targeting IL-17 or the IL-17 receptor	No prior use allowed
Ustekinumab	No prior use allowed
Alefacept, briakinumab, efalizumab	6 months
Biological immunomodulating agents other than the above:	
Etarnecept	3 weeks
Adalimumab	6 weeks
Infliximab	12 weeks
Golimumab	8 weeks
Other systemic immunomodulating treatments [e.g., MTX, cyclosporine A, corticosteroids (oral, i.v., intramuscular, s.c., intra-articular, transdermal), cyclophosphamide]	4 weeks
Other systemic psoriasis treatments (e.g. retinoid, fumarates)	4 weeks
Photo chemotherapy (e.g. PUVA)	4 weeks
Phototherapy (e.g., UVA, UVB)	2 weeks
Topical treatment that is likely to impact signs and symptoms of psoriasis (e.g. vitamin D analogues, pimecrolimus, retinoids, salicylvaseline, salicylic acid, lactic acid, tacrolimus, tar, urea alpha-hydroxy or fruit acids)	2 weeks

Live virus vaccinations	6 weeks
Any investigational treatment or participation in any interventional trial	4 weeks or 5 half-lives (whichever is longer)
Prohibited regimen of Topical Corticosteroids (TCS):	
TCS higher than moderate potency on any body location	2 weeks
TCS mild to moderate potency on any body location other than the face, scalp and or genitoanal area	2 weeks
TCS mild to moderate potency on the face, scalp and or genitoanal area	1 day

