5.5.12 Early study termination

The study can be terminated at any time for any reason by Novartis. Should this be necessary, the patient should be seen as soon as possible and treated as a prematurely withdrawn patient. The investigator may be informed of additional procedures to be followed in order to ensure that adequate consideration is given to protect the patient's interests. The investigator will be responsible for informing Ethics Committees (ECs) of the early termination of the trial.

The study extension can be terminated by Novartis for any reason after a period of at least 12 weeks. Termination may occur only in selected regions where the drug is commercially available; this decision will be made on a region-by-region basis, as for some regions the study will continue as planned even though secukinumab may have become commercially available.

6 Visit schedule and assessments

Table 6-1 lists all of the assessments and indicates with an "x" when the visits are performed. All data obtained from these assessments must be supported in the patient's source documentation.

Patients should be seen for all visits on the designated day. A time window of ± 2 days for weekly visits and ± 7 days for the monthly visits is allowed.

Patients who discontinue the investigational treatment should also return for the assessments in Table 6-1. If they refuse to return for these assessments or are unable to do so, every effort should be made to contact them or a knowledgeable informant by telephone, reporting it in the source documents.

At a minimum, patients will be contacted for safety evaluations during the 30 days following the last study visit, including a final contact at the 30-day point. Documentation of attempts to contact the patient should be recorded in the source documentation.

Table 6-1: Assessment schedule (core study)

Visit	1	2	3	4	5	6	7	8	9	10	11	12/EoS
Week (relative to baseline)	-4	-2	0 (± 2 days)	1 (± 2 days)	2 (± 2 days)	3 (± 2 days)	4 (± 2 days)	8 (± 7 days)	12 (± 7 days)	16 (± 7 days)	20 (± 7 days)	24 (± 7 days)
Day	-28	-14 to -7	1	7	14	21	28	56	84	112	140	168
Informed consent	X											
Demographic data		X										
Inclusion/Exclusion criteria		X	X									
Smoking history		X										
Medical History		X										
TNF α - 308 polymorphism	X											
Psoriasis: medical history		X										
Previous Psoriasis therapies		X										
Quantiferon TB-Gold (within 3 months)		X										
Physical Examination		X	X	X	X	X	X	X	X	X	X	X

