6.5.6 Pregnancy and assessments of fertility

A serum pregnancy test will be performed at visit 2 in all fertile women.

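### Mandatory pregnancy reporting stops with treatment, while the protocol's contraception requirement runs 16 weeks longer

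*Protocol*

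**What the plan says.** Four parts of the protocol bear on this, and the SAP does not mention pregnancy.

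- Section 4.2, criterion 22: women of childbearing potential "must use effective contraception during the study and for 16 weeks after stopping treatment".
- Section 7.4: "each pregnancy occurring while the patient is on study treatment must be reported to Novartis within 24 hours of learning of its occurrence". Follow-up to outcome is attached to the same duty. No post-treatment interval is named.
- Section 6, text before Table 6-1, on the least contact required: "patients will be contacted for safety evaluations during the 30 days following the last study visit, including a final contact at the 30-day point".
- Section 7.2: all serious adverse events are reportable up to 30 days after the last study visit. After that, "Any SAEs experienced after the 30-day period should only be reported to Novartis if the investigator suspects a causal relationship to study treatment".

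Three further provisions matter for the size of the gap. Section 7.1 counts a congenital anomaly or birth defect as a serious adverse event, and it has patients told to report later events that they or their physician think may be related to treatment. Section 5.5.4 and Table 6-1 place a dose at visit 12, which is also the end-of-study visit for patients not entering the extension. Section 6 asks patients who discontinue treatment to keep returning for the Table 6-1 assessments.

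**The concern.** The protocol asks women to avoid pregnancy for 16 weeks after treatment stops, but it does not oblige the site to report or follow a pregnancy that begins in those weeks. A site that followed section 7.4 exactly could learn of such a pregnancy, leave it unreported, and be fully compliant. The study report could then state correctly that no reportable pregnancy occurred, and a reader would not know that the reporting window was shorter than the contraception window.

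Pregnancies after exposure are likely to be few, so each lost outcome matters, and data not collected cannot be recovered at analysis. What is at stake is the completeness of the safety data, not any efficacy result.

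**Working it through.** The plan gives no figure of its own to reproduce. The check is day arithmetic on the stated windows.

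**Inputs.** Contraception after stopping treatment: 16 weeks (criterion 22). Minimum contact: 30 days after the last visit (section 6). Visit days: week 16 = day 112 and week 24 = day 168 (Table 6-1); week 72 = day 504 (SAP Table 2.1). Extension dosing: every 4 weeks for 48 weeks (section 5.5.4), with the day of the last dose not fixed. 48/4 = 12 doses. If the first falls at week 24, the last is at 24 + 11 x 4 = week 68; if the first falls at week 28, the last is at 28 + 11 x 4 = week 72. Both are shown.

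**Step 1, reporting duty.** Post-treatment window = 16 x 7 = 112 days. Section 7.4 names no post-treatment days, so 0 of 112 are covered. The term for being on treatment is not defined there. If a site read it as lasting one 4-week dosing interval beyond the last injection, while counting the contraception period from the injection, 28 days would be covered and 112 - 28 = 84 (75%) would not. Neither reading reaches 16 weeks.

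**Step 2, scheduled contact.** Days inside contact = min(112, last visit day + 30 - last dose day). Days outside = 112 minus that.

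| Case | Last dose day | Last visit day | Inside | Outside | Share outside |
|---|---|---|---|---|---|
| Core completer, dosed at week 24 visit | 168 | 168 | 30 | 82 | 73% |
| Extension completer, last dose week 72 | 504 | 504 | 30 | 82 | 73% |
| Extension completer, last dose week 68 | 476 | 504 | 58 | 54 | 48% |
| Same, visit 7 days early | 476 | 497 | 51 | 61 | 54.5% |
| Same, visit 7 days late | 476 | 511 | 65 | 47 | 42% |
| Stops at week 16, dosed that day, no later visit | 112 | 112 | 30 | 82 | 73% |
| Stops at week 16, last dosed week 12, no later visit | 84 | 112 | 58 | 54 | 48% |
| Stops at week 16, dosed that day, attends to week 24 | 112 | 168 | 86 | 26 | 23% |
| Stops at week 16, last dosed week 12, attends to week 24 | 84 | 168 | 112 | 0 | 0% |

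**Step 3, other routes.** The late rule in section 7.2 reaches a birth defect or other serious event if the investigator suspects a link. The patient instruction in section 7.1 reaches events believed to be related. A pregnancy without complications is neither, so no rule outside 7.4 makes it reportable.

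**The case against.** The strongest reply is that the post-treatment interval is not empty. The 30 days are a minimum, they run from the last visit and not the last dose, and patients who stop early are asked to keep attending. Patients are told to report later events they think related, and a suspected related birth defect has no time limit. All of this is correct. A reader might infer that the whole 16 weeks goes unwatched, and the documents do not support that. What remains is narrower: none of these routes requires a report of an uncomplicated pregnancy or its follow-up to outcome.

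A reader might also take criterion 22 as the protocol's definition of a period of fetal risk. The criterion is a contraception condition and does not use that language; the link is an inference.

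Two nearby texts invite stronger claims that do not hold up. Section 6.5.6 says "A serum pregnancy test will be performed at visit 2 in all fertile women", and Table 6-1 schedules no later test, while section 5.5.9 makes pregnancy a reason to stop treatment. These do not conflict, since a rule for action once pregnancy is known does not promise scheduled testing. Section 5.5.8 says that a patient given a live virus vaccine "he/she must discontinue study treatment and enter the post-treatment follow up period". That period has no schedule under its own name, but the sentence covers all patients, men included, and section 6 already tells those who discontinue which assessments to attend. A pregnancy contact would not be a sensible replacement for it.

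Finally, the consent form is a separate document (section 10.2) and is not available here, so what patients are told about pregnancy after the study cannot be checked. Consent wording would not alter the investigator's duty under 7.4.

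**Conclusion.** The mismatch stands in the current text. With both windows counted from the last dose, mandatory pregnancy reporting covers none of the 112 post-treatment days, whichever way a patient leaves treatment.

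The share without scheduled contact varies. It is 73% where last dose and last visit coincide, about 48% (42% to 54.5% across the visit window) if the last extension dose is at week 68, and 0% to 23% for week-16 stoppers who attend to week 24. The 73% should not be read as general: about 306 of the 406 patients are planned for the extension, where the last dose day is open.

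The number of women affected cannot be stated, because the documents do not say how many participants are of childbearing potential. The conclusion does not depend on it. The gap concerns safety reporting only and leaves the primary PASI 90 analysis untouched. It merits correction because the rule, followed exactly, loses safety information and is cheap to change.

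**What to change.** Reconcile criterion 22, section 6 and section 7.4. Extend the reporting and outcome follow-up duty in 7.4 to pregnancies occurring during treatment or during the post-treatment contraception period, by cross-reference to criterion 22 (now 16 weeks after stopping treatment), using the same pregnancy form. State in both places the day from which the period is counted. This aligns reporting with the period the protocol already states; it takes no position on how long contraception should last.

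Optionally, add one telephone contact in section 6 at the end of that period for women of childbearing potential. Without it, the wider duty relies on pregnancies being volunteered after the 30-day contact.

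The cost is a change of wording, a check that the consent form agrees, and, if the call is added, a small amount of extra site work. No visit, procedure or change to treatment is needed.
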